### 14.4 Collection and Recording of Adverse Events

#### 14.4.1 Collection Period

During Stage 1, AEs will be collected from the time of first study procedure (leukapheresis or 450-500 ml blood draw), until 72 hours after completion of the leukapheresis procedure or 450-500 ml blood draw. AEs occurring outside the 72 hour window should be reported if the investigator deems a possible association with the protocol mandated leukapheresis or blood draw.

During Stages 2 and 3 (including Cohort 1 follow up), AEs will be collected from the time of first Thymoglobulin® administration, until a subject completes study participation or until 30 days after he/she prematurely withdraws (without withdrawing consent) or is withdrawn from the study.

Additionally, elevated liver tests (i.e. ALT, AST, ALP, GGT, and bilirubin) must be reported starting 7 days after transplant. Events involving unexpected elevations of liver tests in the first week should be reported according the site investigator's judgment.

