Accrual Objective	
 
18 - 24 subjects:
 
Cohort 1: 3 subjects from Center 1 (Cohort 1a) + 3 subjects from Center 2 (Cohort 1b)
 
Cohort 2: At least 3, and up to 6 subjects (Dose A)
 
Cohort 3: At least 3, and up to 6 subjects from either Center (Dose B)
 
Cohort 4: 6 subjects from either Center (Dose C).
 

Study Duration	4 year accrual period, 40 weeks of follow-up after transplantation

Confidential Page 4 of 80

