Study Termination	Subjects who complete the study, are lost to follow up, withdraw consent, or die during the study. Data and specimens will no longer be expected from subjects who are terminated from the study.			
Study Therapy	The investigational agents (darTregs and Thymoglobulin®) and all protocol required medications.			
Withdrawal from Therapy	Subject who stops study therapy prior to protocol described duration.			

Confidential Page 18 of 80

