#### 3. Study Design

#### 3.1 Description of Study Design

This is a multi- center, open-label, dose- escalation, pilot study in which adult subjects undergoing primary solitary liver transplant will receive a T cell depletion agent (Thymoglobulin®) followed by Treg-supportive IS regimen based on either EVR or reduced-dose TAC (Cohorts 1a and 1b). Subjects in subsequent cohorts will also receive a single infusion of autologous, darTregs (Cohort 2: 50 million darTregs; Cohort 3: 200 million darTregs: or Cohort 4: 800 million darTregs). For individual participants, there are up to three successive stages in the study with specific eligibility criteria for each stage. As shown in *Figure* 8, the three stages are:

- Screening and Enrollment
- Eligibility assessment for EVR conversion and proceeding to T-reg infusion
- darTreg Infusion

Subjects will be followed for 40 weeks after transplant, during which clinical data along with peripheral blood (PBMCs and serum) and liver biopsy samples will be collected and analyzed (Appendix 1, 2 3).

[figure not shown]

Figure 8. Three Stages of Trial

The four cohorts are summarized below, with details about the dose escalation plan in Section 5.4.

- Cohort 1: 3 subjects from Center 1 (Cohort 1a) + 3 subjects from Center 2 (Cohort 1b); these subjects will undergo T cell depletion followed by TAC- or EVR-based IS (Stage 1 and 2; they will not receive darTreg infusion (Stage 3)).
- Cohort 2: 3 subjects meeting eligibility criteria for all 3 Stages will receive 50 million darTregs (Dose A range 25-60 million).
- Cohort 3: 3 subjects meeting eligibility criteria for all 3 Stages will receive 200 million darTregs (Dose B range 100-240 million).
- Cohort 4: 6 subjects meeting eligibility criteria for all 3 Stages will receive 800 million darTregs (Dose C range 400-960 million).

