# **5.4.3** Rationale for Staggering Intervals

All participants in Cohort 1a – those who receive Treg supportive IS alone - must be monitored for 12 weeks prior to enrollment of Cohort 2 and Cohort 1B by the second clinical site. The rationale for selecting 12 weeks is that this interval covers the time period that has the highest incidence of important post-liver transplant complications such as rejection and infection, particularly bacterial and fungal infections related to the transplant operation including those directly related to the transplant incision / wound.

Within each darTreg dosing cohort, there is a mandatory four-week observation period after the administration of darTregs to the 1st patient of each cohort before the 2nd patient can receive darTregs. We have selected a shorter observation time interval for several reasons. First, darTregs will be administered sometime between Week 11-20 after transplant. This is a period of relative clinical quiescence that will readily permit optimal identification of AEs that may be precipitated by the darTreg infusion. Liver transplant recipients have largely recovered from the transplant operation as well as from the baseline liver disease. They continue on anti-viral (until 6 months after transplantation) and anti-

Confidential Page 40 of 80

pneumocystis prophylaxis (until at least 12 months after transplantation) such that the frequency of these infections is very low. Second, we anticipate that the majority of complications associated with darTreg administration (infusion reaction, AR, or infection) are most likely to occur early, soon after administration while the beneficial effect of darTreg administration may well evolve and/or intensify over time. Infection may be precipitated by contamination of the darTreg preparation with infectious agents or with non-donor-alloantigen-reactive Tregs that lead to generalized over-immunosuppression. Similarly, rejection may be precipitated by contamination of the darTreg preparation with T effector cells. In these cases, the deleterious impact of darTreg infusion is expected to manifest soon – within 4 weeks – after infusion. While malignant transformation of infused cells is a concern, the timeframe of this complication as well as its manner of presentation is certainly difficult if not impossible to predict and therefore, this safety concern cannot be mitigated by any sort of mandatory waiting period.

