# 10.3 Follow-up for Cohorts 1a and 1b

Participants enrolled in Cohorts 1a and 1b who will not receive darTreg infusion will follow Appendix 2. Recipient Schedule of Events (Cohort 1a and 1b) starting at week 12 after transplantation. Visits to the transplant center will take place at week 12, 16, 24 and 40 after transplantation. Laboratory assessments will take place every 4 weeks until the end of the study, 40 weeks after transplantation. Please refer to Appendix 2. Recipient Schedule of Events (Cohort 1a and 1b Follow Up)

Confidential Page 50 of 80

### 10.4 Stage 3: darTreg Infusion for Cohorts 2, 3, and 4

Participants enrolled in Cohorts 2, 3, and 4 must undergo the following study procedures and visits. darTreg infusion will take place between weeks 11-20 after liver transplantation and will require an overnight stay. Screen D eligibility must be met. Blood for central laboratory assessments will be drawn prior to the infusion and 24 hours after the infusion is complete. Visits to the transplant center will take place 1 week and 4 weeks after darTreg infusion as well as 12 and 28 weeks after darTreg infusion (approximately 24 and 40 weeks after transplantation, respectively). A liver biopsy will be done in conjunction with the visit 1 week after darTreg infusion. Thereafter, laboratory assessments must take place every two weeks for 10 weeks, followed by every 4 weeks until the end of the study, 28 weeks after darTreg infusion, or 40 weeks after transplantation. Details regarding study procedures including monitoring, laboratory assessment, and blood draws for mechanistic studies are specified in *Appendix 1. Recipient Schedule of Events (Stage 3: Cohorts 2, 3, and 4)*.

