# 14.8.1 Study Stopping Rules

The decision to pause enrollment pending DSMB review will be based on the occurrence of selected SAEs described below:

1. Death or graft loss

Confidential Page 61 of 80

- 2. Infections of Grade ≥3 as defined in Section 14.3.1
- 3. Severe AR
  - a. Histological: according to 1997 Banff criteria (Demetris A. D., 2000)
  - b. Clinical: steroid refractory rejection (see Study Definitions)
- 4. CR (early or late) according to 2000 Banff criteria (Demetris A. J., 1997)
- 5. PTID
- 6. Malignancy excluding recurrent HCC and skin cancer
- 7. CTCAE  $\geq$  3 Infusion reaction
- 8. Failure to manufacture and supply the cellular product for 2 subjects.

Since the trial is small and these events are of particular concern, and the risks are expected to be different in the two stages of the trial, absolute thresholds for the numbers of such events have been established for each event in each stage that would satisfy the stopping rule.

Table 7. Minimum Numbers of Selected AEs in each Stage that would Satisfy the Stopping Rule

Selected SAE	Lymphocyte Depletion/Treg Supportive IS Stage 2	darTreg Infusion Stage 3
Death or graft loss	1	1
Grade ≥3 Infection (Section 14.3.1)	1	1
Severe AR (histological or steroid refractory rejection)	2	1
CR	1	1
PTLD	1	1
Malignancy excluding recurrent HCC and in situ skin cancer	1	1
CTCAE ≥ 4 Infusion reaction	N/A	1

Every patient who initiates Stage 2, defined as receiving any amount of a Thymoglobulin® infusion, will contribute to the assessment of the safety of Treg supportive IS. At the point in time when the patient initiates Stage 3, defined as receiving any amount of a darTreg infusion, he/she will contribute to the safety assessment for darTreg infusion. Any death or Grade ≥3 infection (defined in Section 14.3.1) occurring in subjects prior to initiation of Thymoglobulin® infusion (prior to Stage 2) will not stop the trial.

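### AE collection stops when an infused subject completes, so late PTLD or malignancy has no required route into the Stage 3 stopping count while later, higher-dose infusions may still be under way

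*Protocol*

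**What the plan says.** Protocol 14.4.1 runs Stage 2 and 3 collection from the first Thymoglobulin dose "until a subject completes study participation or until 30 days after he/she prematurely withdraws". Section 14.4.4 follows a recorded event no further than the end of participation. The Study Definitions page counts completers among terminated subjects and adds: "Data and specimens will no longer be expected from subjects who are terminated from the study".

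For Stage 1 the same section goes beyond its fixed window: "AEs occurring outside the 72 hour window should be reported if the investigator deems a possible association" with the leukapheresis or blood draw. There is no counterpart for the cell product.

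On duration, section 3.1 says "Subjects will be followed for 40 weeks after transplant", and section 10.4 says "darTreg infusion will take place between weeks 11-20 after liver transplantation". Section 10.4 also places the end of study at 28 weeks after infusion, as do Appendix 3 and section 15.6.

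On monitoring, section 14.8.1 states that "absolute thresholds for the numbers of such events have been established for each event in each stage". Table 7 sets the Stage 3 threshold at 1 for PTLD and 1 for malignancy. Section 14.8.1 says when a subject begins to count in Stage 3 but gives no end. Safety outcome 5 includes malignant cellular transformation, of which section 5.4.3 says "the timeframe of this complication as well as its manner of presentation is certainly difficult if not impossible to predict".

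**The concern.** The two slowest hazards in Table 7 have single-event thresholds with no time limit, but the data feeding them stop at completion. Section 5.4.3 accepts that no waiting period can deal with malignant transformation because its timing is unpredictable. That argues for keeping a reporting line open, and none is provided. A blood draw thus has an open-ended reporting clause that a new cell product lacks.

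At stake is whether a PTLD or malignancy arising in an early, lower-dose subject after completion reaches the stopping count before later subjects receive doses 4 times (200 against 50 million) or 16 times (800 against 50 million) higher. The point concerns subjects who complete. It is separate from the follow-up of subjects who withdraw.

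**Working it through.** **The plan's own figure.** Section 15.6 plans 12 infused subjects × 28 weeks = 336 person-weeks. The 28 weeks equal 40 − 12, an infusion at week 12. Table 8's row for 2 events in 336 person-weeks (0.0060; 0.0007 to 0.0215) reproduces with exact Poisson limits.

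**Length of collection after infusion.** If 40 weeks after transplant governs, it is 40 − 20 = 20 weeks to 40 − 11 = 29 weeks. If the visit at 28 weeks after infusion governs, it is 28 weeks for everyone, ending at week 11 + 28 = 39 to 20 + 28 = 48 after transplant. The two agree only for an infusion at week 12.

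**Inputs for timing.** There are 12 infusions: 3 in Cohort 2, 3 in Cohort 3 and 6 in Cohort 4 (section 3.1). The pace of 4 to 5 a year comes from section 4.4, which gives it in describing UCSF. Applying it to the whole trial, evenly spaced, is an assumption. Rates of 8 and 10 a year represent a doubled pace with other centres contributing.

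**Formulas.** Spacing d = 52/rate. The last infusion is at T = 11d after the first. Infused subjects' time up to T is d × (0 + 1 + … + 11) = 66d. Covered time is the sum over subjects of min(w, T − tᵢ), where w is the collection window. The three Cohort 2 infusions precede the first Cohort 4 infusion by 6d, 5d and 4d.

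**Covered time with w = 28 weeks.**
- 4 a year, d = 13: 9 × 28 + 26 + 13 + 0 = 291 of 858, or 34%.
- 5 a year, d = 10.4: 9 × 28 + 20.8 + 10.4 + 0 = 283.2 of 686.4, or 41%.
- 8 a year, d = 6.5: 7 × 28 + 26 + 19.5 + 13 + 6.5 + 0 = 261 of 429, or 61%.
- 10 a year, d = 5.2: 6 × 28 + 26 + 20.8 + 15.6 + 10.4 + 5.2 + 0 = 246 of 343.2, or 72%.

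| Infusions a year | First to last infusion (weeks) | Cohort 2 infusions to first Cohort 4 infusion (weeks) | Cohort 2 subjects still in collection then (w = 28) | Covered share, w = 28 | Covered share, w = 20 to 29 |
|---|---|---|---|---|---|
| 4 | 143 | 78, 65, 52 | 0 of 3 | 34% | 25-35% |
| 5 | 114.4 | 62.4, 52, 41.6 | 0 of 3 | 41% | 31-43% |
| 8 | 71.5 | 39, 32.5, 26 | 1 of 3 | 61% | 46-62% |
| 10 | 57.2 | 31.2, 26, 20.8 | 2 of 3 | 72% | 56-73% |

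The extremes at 4 to 5 a year are 213/858 = 25% (4 a year, w = 20) and 292.2/686.4 = 43% (5 a year, w = 29). With w = 28, uncollected time up to the last infusion is 858 − 291 = 567 or 686.4 − 283.2 = 403.2 person-weeks, and 9 of the 11 earlier subjects have left collection before the last infusion.

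**Faster schedules.** With a steady 4-week spacing, T = 44 weeks. Then 4 earlier subjects (w = 28) to 6 (w = 20) are out before the last infusion. At the fastest spacing section 5.4.2.2 permits (a 4-week wait only after the first subject of each cohort), all 12 infusions fit within 12 weeks and nobody leaves collection before the last one.

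**The case against.** A reader might infer that late events cannot trigger a hold or reach the DSMB. The documents do not support that.
- Section 14.7 obliges investigators to notify the coordinating center, which monitors the stopping criteria, of unanticipated problems not otherwise reportable. A malignancy attributed to a new cell product could well qualify.
- Section 14.8 provides ongoing review with power to suspend. Section 14.8.3 allows ad hoc DSMB review, and SAP section 7 foresees DSMB review of events that could contribute to a stopping rule.
- Section 14.5.1 requires SAEs within 24 hours of discovery and names no end date.

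These routes are real but partial. Section 14.7 turns on a judgment about each event, ad hoc review depends on someone asking for it, and neither is linked to the Table 7 count. Section 14.5.1 sets reporting speed; 14.4.1 sets the period.

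It is also fair that the Stage 1 clause offsets a window of only 72 hours, whereas Stage 3 has months of continuous collection. The contrast shows that suitable wording exists; it does not prove an oversight. The outcomes are openly defined within 40 weeks of transplant, and no passage promises later collection.

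The size depends on pace. Section 4.4 treats its enrolment figure as a minimum and calls outside centers critical. That every Cohort 2 subject has left before Cohort 4 begins is therefore not a general fact: with a 28-week window it fails at 8 to 10 infusions a year.

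Finally, counting every late death, graft loss or chronic rejection of any cause against a threshold of 1 could halt the trial for unrelated events, since completers may return to site-standard immunosuppression (section 13.1). That objection stands and limits the remedy.

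**Conclusion.** The concern holds in a limited form. As written, a PTLD or malignancy first found after an infused subject completes has no required collection route into the Stage 3 column of Table 7, while later subjects may still be receiving higher doses. The text alone establishes this.

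The size rests on two assumptions: evenly spaced infusions, and a UCSF-based pace applied to the whole trial. At 4 to 5 a year about a third to two-fifths of the relevant time is covered with a 28-week window, and Cohort 2 is wholly out of collection before Cohort 4 starts. At double that pace most of the time is covered and one or two Cohort 2 subjects remain in collection. The gap vanishes only on a schedule far faster than the plan's own "4 year accrual period, 40 weeks of follow-up after transplantation" suggests. This is a cheap improvement to safety reporting; it does not undermine the planned 40-week analyses.

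**What to change.** 1. **Protocol 14.4.1.** Add that, until the last infused subject completes, sites report any PTLD, any malignancy within the Table 7 definition, and any SAE judged possibly related to darTregs that they become aware of in an infused subject who has completed. Align the Study Definitions page. The malignancy exclusion must first be made consistent: the list in 14.8.1 excludes skin cancer, Table 7 only in situ skin cancer.
2. **Protocol 14.8.1.** State that such late PTLD and malignancy events count in the Stage 3 column. Send other late related SAEs, including deaths, graft losses or chronic rejection, to the medical monitor and DSMB for ad hoc review without an automatic hold.
3. **SAP 9.3.** List these events separately, outside the 40-week rates.
4. **Protocol 10.4.** Reconcile the two end-of-study definitions, so that the date of completion is unambiguous.

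The cost is a few sentences and possibly consent wording, with no added visits, tests or staff. Reporting would be passive, so these events cannot enter the incidence rates and a lack of reports would be weak reassurance. A late malignancy unrelated to darTregs could cause a temporary hold pending DSMB review.

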# 14.4.2 Collecting Adverse Events

AEs (including SAEs) may be discovered through any of these methods:

- Observing the subject
- Interviewing the subject [e.g., using a checklist, structured questioning, diary, etc.]
- Receiving an unsolicited complaint from the subject

In addition, an abnormal value or result from a clinical or laboratory evaluation can also indicate an AE, as defined in Section 14.3 Grading and Attribution of AEs.

### 14.4.3 Exceptions to Collection

Elective hospitalizations, hospitalization solely for a diagnostic procedure, or hospital admissions to conduct protocol mandated procedures are not to be collected as an AE unless hospitalization is prolonged due to complications.

# 14.4.4 Recording Adverse Events

Throughout the study, the investigator will record AEs and SAEs as described previously (*Section 14.2, Definitions*) on the appropriate AE/SAE form regardless of the relationship to study therapy regimen or study procedure.

Confidential Page 59 of 80

Once recorded, an AE / SAE will be followed until it resolves with or without sequelae, until the end of study participation, or until 30 days after the subject prematurely withdraws (without withdrawing consent) /or is withdrawn from the study, whichever occurs first.

#### 14.5 Reporting of Serious Adverse Events and Adverse Events

# 14.5.1 Reporting of Serious Adverse Events to Sponsor

This section describes the responsibilities of the site investigator to report SAEs to the sponsor via the Statistical and Clinical Coordinating Center (SACCC) eCRF. Timely reporting of AEs is required by 21 CFR and ICH E6 guidelines.

Site investigators will report all SAEs to the sponsor, regardless of relationship or expectedness within 24 hours of discovering the event.

For SAEs, all requested information on the AE/SAE form should be provided. However, unavailable details of the event will not delay submission of the known information. As additional details become available, the AE / SAE should be updated and submitted.

#### 14.5.2 Reporting to Health Authority

After an AE requiring 24 hour reporting (13.5.1, *Reporting of SAEs to Sponsor*) is submitted by the site investigator and assessed by DAIT/NIAID, there are two options for DAIT/NIAID to report the AE to the health authority:

# 14.5.2.1 Annual Reporting

DAIT/NIAID will include in the annual study report to health authorities all AEs classified as:

- Serious, expected, suspected adverse reactions (Section14.2.2, Suspected Adverse Reaction, and Unexpected AE)
- Serious and not a suspected adverse reaction (Section 14.2.2, Suspected Adverse Reaction)
- Pregnancies not reported as SAEs

Note that all AEs (not just those requiring 24-hour reporting) will be reported in the Annual IND Report.

# 14.5.2.2 Expedited Safety Reporting

This option, with 2 possible categories, applies if the AE is classified as one of the following:

**Category 1**: **Serious and unexpected suspected adverse reaction [SUSAR]** (*Section 14.2.1.1, Suspected Adverse Reaction* and Section 14.2.2, *Unexpected AE* and 21 CFR 312.32(c)(1)i).

The sponsor shall report any suspected adverse reaction that is both serious and unexpected. The sponsor shall report an AE as a suspected adverse reaction only if there is evidence to suggest a causal relationship between the study drug and the AE, such as:

- 1. A single occurrence of an event that is uncommon and known to be strongly associated with drug exposure (e.g., angioedema, hepatic injury, or Stevens-Johnson Syndrome);
- 2. One or more occurrences of an event that is not commonly associated with drug exposure, but is otherwise uncommon in the population exposed to the drug (e.g., tendon rupture);
- 3. An aggregate analysis of specific events observed in a clinical trial (such as known consequences of the underlying disease or condition under investigation or other events that commonly occur in the study population independent of drug therapy) that indicates those events occur more frequently in the drug treatment group than in a concurrent or historical control group.

# Category 2: Any findings from studies that suggests a significant human risk

The sponsor shall report any findings from other protocols, epidemiological studies, analyses of AEs within the current study or pooled analysis across clinical studies or animal or *in vitro* testing (e.g. mutagenicity, teratogenicity, carcinogenicity) that suggest a significant risk in humans exposed to the drug that would result in a safety-related change in the protocol, informed consent, investigator brochure or package insert or other aspects of the overall conduct of the study.

Confidential Page 60 of 80

DAIT/NIAID shall notify the FDA and all participating site investigators of expedited Safety Reports within 15 calendar days; unexpected fatal or immediately life-threatening suspected adverse reaction(s) shall be reported as soon as possible or within 7 calendar days.

